2.0 Identification and description of the investigational device

Cochlear implant device introduction

Each Advanced Bionics cochlear implant system operates with an implantable portion, and external sound processor, and headpiece that acts as a communication link between the implant and sound processor. These devices, including both internal and external components, have been authorized by the FDA and other Regulatory bodies for commercial distribution. As these implant systems have become more widely distributed and technology evolves, increased data and user feedback as well as component obsolescence issues mandate that new designs for external devices be developed for use with existing cochlear implant systems.

Cochlear implant headpieces allow sound processors to transmit audio information and power through a recipient's skin to power the internal implant and supply the audio source that is electrically reproduced for hearing. The headpiece is worn on the head, sitting on the hair or scalp in a position behind and slightly above the ear. The headpiece contains a magnet that is attracted to a second magnet embedded under the skin in the internal implant, the attraction between these two magnets provides retention to the head.

The current, commercially approved, [REDACTED] addresses clinical needs expressed by customers: retention, irritation, and aesthetics. [REDACTED] P design allows for user-adjustability of the headpiece magnet strength, allowing up to a maximum of five full-strength magnets to be used with the [REDACTED] or as few as one magnet. Changing the number of magnets and distance between magnets allows one to change retention strength. Cochlear implant recipients will have different thickness of skin and hair between the case of the implant and the external headpiece; for this reason, there is a need to individualize the selection of magnets to find a retention strength that holds the headpiece in place during daily activities, while remaining comfortable.

Description of the investigational device and design options

- **Investigational Headpiece:** All investigational headpieces used in this study will use the same electrical components and biocompatible materials as the commercially available, FDA-approved headpieces distributed by Advanced Bionics. The investigational headpieces will have design modifications to molded materials (e.g. plastic, rubber, silicone or Teflon) to address cosmetic issues (e.g. mold flash or mold sink) or design improvements resulting from subject feedback. The investigational headpieces will have possible modifications to the headpiece magnet type/material used. Prior to subject use, the investigational device shall

Non-Significant Risk Study of a Cochlear Implant Headpiece

- be subject to stimulation safety and integrity testing, electrical testing, safe temperature profiling and materials biocompatibility testing.
- **Implantable Systems:** All cochlear implant recipients enrolled in the study will be current users of an FDA approved cochlear implant manufactured by Advanced Bionics.
- **External Wearable Cochlear Implant Sound Processors:** All Advanced Bionics implantable systems operate in conjunction with a number of externally worn, FDA-approved, sound processors and headpieces. Subjects enrolled in the study will be current users of these commercially available sound processors.
- **Directions for Use:** Participants who have a cochlear implant will have already been implanted with a device manufactured by Advanced Bionics independently of this study and according to standard medical practice and will be familiar with the usage of their own clinically approved standard devices.

3.0 Design of the clinical investigation

3.1 Study Objective

- The objective of this study is to evaluate an investigational cochlear implant headpiece for individuals who are current users of FDA approved Advanced Bionics cochlear implants. This investigational headpiece and the compatible magnet is expected to provide acceptable comfort and retention for existing cochlear implant users. In this study, participants will subjectively report on their experience with the investigational headpiece during daily life.

3.2 Study Investigators and Study Staff

- The investigational site team for this study consists of clinical, research and field staff employed by the sponsor. At all study activities, at least one Investigator or Study Staff will be available to supervise conduct. All study Investigators and Study Staff will receive training specific to the study protocol and their study responsibilities.

3.3 Management and recruitment of study participants

Recruitment

- Participants who meet the study criteria will be recruited from cochlear implant recipient populations across North America. A participant's willingness and ability to meet the follow-up requirements will be determined and informed consent will be obtained. Participants under the age of 18, will be consented through a parent or guardian and provided a complementary assent, with age specific language for children ages 7-12 years and children ages 13-17 years. A signed and dated copy of this consent will be kept in the participant's study record and copy provided to the participant.

Participant Screening

- No investigational procedures are used to screen participants for study eligibility. Participants eligible to participate in this study will be evaluated according to the inclusion requirements for the study. Informed consent will be obtained before any study-specific tests or procedures are conducted. An individual is considered to be enrolled as a study participant only after the informed consent document has been signed and dated. Each participant will be assigned a unique identifier at the time of enrollment.

Inclusion criteria for participant selection

- Pre- or post-lingually deafened.
- Fluent in English, French, or Spanish or capable of communication with a caregiver who is providing consent.

Non-Significant Risk Study of a Cochlear Implant Headpiece

- Adult or child implanted with a commercially available Advanced Bionics cochlear implant. Children and adult participants are included to ensure device retention is appropriate for all implant populations.
- Have (or caregivers have) the cognitive and functional capability to comply with all directions during the study
- Be able to remove their own headpiece
- Have (or caregivers have) the cognitive and functional capability to complete the questionnaire required for the study
- Capable (or caregivers are capable) of reading and understanding patient information materials and giving written informed consent

Exclusion criteria for participant selection

- Have any significant medical condition that, in the opinion of any of the investigators, is likely to interfere with study procedures or likely to confound evaluation of study data.

Criteria and procedures for participant withdrawal or discontinuation

- Participants may withdraw from the study at any time, with or without reason, and without affecting continued standard of medical care they would receive.
Participants can be discontinued from the study for the following reasons:
 - Withdrawal of consent
 - A safety concern noted by a clinician that endangers the participant or cannot be tolerated for medical and/or ethical reasons
 - Inability of the participant to perform the tasks necessary to provide usable data for the study.
- The Investigator or Study Staff will complete a log to document the disposition of each enrolled participant (completed study, withdrew, discontinued). Any withdrawal or discontinued participation will be documented.

Consent

- Participants should appear to meet all of the eligibility criteria and none of the criteria for ineligibility before they are asked to consent to continue with study-specific screening procedures. Written informed consent must be obtained for all people who are potential study candidates before any study-specific tests or procedures are performed.
- Study candidates who meet general entry criteria will be asked to sign the Institutional Review Board (IRB) approved Informed Consent form before any study-specific tests or procedures are performed. Study personnel should explain that even if a patient agrees to participate in the study and signs an informed consent form, certain diagnostic or screening procedures might demonstrate that the patient is not eligible to continue participation. Examples of situations that may lead to

Non-Significant Risk Study of a Cochlear Implant Headpiece

exclusion from further participation are the presence of exclusionary medical or psychological conditions or a condition that might confound study results.

- Investigators or the Study Staff and the candidate for consent will share English, Spanish, or French language fluency.
- For study activities conducted in the State of California, research subjects will also be provided with the California Experimental Subject's Bill of Rights.

Point of enrollment

- An individual is considered to be enrolled as a study participant only after completion of the informed consent. Each participant will be provided ample time to consider participation in the trial. Once enrolled, the participant will be assigned a unique identifier. [REDACTED]

[REDACTED]

Total expected duration of the clinical investigation

- The present study is expected to continue at least for one year from initiation or until the investigational headpiece receives FDA approval, whichever comes last.

Expected duration of participation

- Duration of participation will vary from the time of enrollment to the one-year end point or until the investigational headpiece receives FDA approval, whichever comes last.

Number of participants required to be included in the clinical investigation

- A minimum of 20 participants will be enrolled in this present study, with a maximum of 200 participants.

3.4 Description of all study procedures

The present study uses a single-group, prospective, within-subjects, repeated measures design, participants will complete questionnaires to provide subjectively reported opinions of investigational headpiece retention and comfort. Questionnaires will be available in English, French, and Spanish. English language examples are provided in Appendix 2.

Candidates for study participation and caregivers or family will be referred by audiologists from audiological and medical centers across the United States and Canada. The audiologist will be informed of this study by local Study Staff and the referral will be made through a telephone call, email, or in-person conversation. All participants will be recipients of commercially available Advanced Bionics' cochlear implants and the commercially available sound processors.

Study staff will contact prospective participants through a telephone call, email, or in-person conversation. A private location will be used for all study activities. Examples of private locations include but are not limited to: a meeting room in a hotel, a meeting room in an office building or clinic, or the participants home. Study staff will consent all participants prior to introduction of the cochlear implant headpiece. Participant contact information will be collected at this time, no other identifying or health-related information will be collected. If the participant is too young or unable to provide consent otherwise, a parent or guardian will complete the consenting process and the participant will be asked to assent to study participation.

Following completion of the informed consent, subjects will be asked to fill out a Baseline Questionnaire answering questions about their current headpiece. After completion of Baseline Questionnaire, Study staff will introduce the investigational headpiece and magnets to the participant. Participants and caregivers will have been previously trained and experienced in the use of their existing cochlear implant headpiece. Study staff will select the appropriate investigational headpiece magnet strength, identifying which magnet strength has appropriate retention. Appropriate retention is subjectively defined as retention sufficient to hold the headpiece in place during activities of daily life, while avoiding discomfort.

Following selection of the headpiece magnet and appropriate fit of the investigational headpiece, the study staff will introduce the Investigational Headpiece questionnaires that participants will complete at the initial visit and two-month intervals throughout their participation in the study. Participants will receive a number of questionnaires that would span the study duration. Pre-paid envelopes will be provided to allow participants to return completed questionnaires every two-months for the duration of the study.

At any time during the study, participants may request meetings with Investigators or Study Staff for changes in magnet strength or adjustments to the investigational headpiece, these meetings will be coordinated through a telephone call, email, or in-person conversation to set up additional visits.

Participants will return the investigational headpiece to the Sponsor at the end of this study. A pre-paid shipping envelope will be provided for this purpose.

Data collection and analysis of the present study will be administered from the Sponsor's location. Recruitment, participant consenting, and fitting of the investigational cochlear implant headpiece may be completed by study staff, with professional training with the Advanced Bionics cochlear implant system, at locations outside of the Sponsor's location. Investigators and study staff will complete training for this study that includes:

- Good Clinical Practice, including investigator responsibilities
- Informed consent procedures, including requirements for inclusion, exclusion, and all foreseeable risks
- Study protocol and procedures
- Processes for recording and reporting adverse events
- Device accountability procedures
- Data collection and correction procedures, source documentation, and record retention requirements

3.5 Documentation and Records

All study records (e.g., protocol, correspondence with the Sponsor and the IRB, IRB approvals, participant contact information, consent forms, reports) will be maintained by the Principal or Sub-Investigators as long as local document retention regulations require. If an Investigator opts to discontinue participation in the study, all records will be transferred to a mutually agreed designee (i.e., another Investigator).

3.6 Compensation

Compensation for participation in this study will include:

- Travel, Parking, and Mileage will be paid by Advanced Bionics
- Meal expenses for the participant and one additional person will be reimbursed by Advanced Bionics. Reimbursement per-meal may not exceed [REDACTED].
- Participants will receive [REDACTED] for participation in this study, with an additional [REDACTED] for each questionnaire received by the Sponsor.
- Payment of [REDACTED] will be sent following the first visit and questionnaire payments will be sent semi-annually afterward.

Non-Significant Risk Study of a Cochlear Implant Headpiece

4.0 Device accountability, risks, and benefits

4.1 Anticipated clinical benefits

- Participants are not expected to experience clinical benefits beyond those present during the use of existing headpieces. Some participants may find that this headpiece offers greater retention, as the investigational headpiece design may allow for increased retention. The clinical benefit of this latter case is more consistent headpiece retention.

4.2 Risks associated with participation in the clinical investigation and mitigation

- Anticipated adverse device effects:** The investigational headpiece has a new bottom profile with respect to the currently approved headpieces. The risks identified below are risks associated with currently FDA-approved headpieces. There are no anticipated new risks associated with the investigational design.

Procedure	Risk	Risk Mitigation
Use of investigational hardware	Wearing the device is uncomfortable, minor skin irritation.	The bottom profile (in contact with patient skin) is functionally similar to previously approved headpiece design.
Use of stronger magnet strength	Skin flap irritation/pain due to excessive pressure. ICS extrusion due to skin flap breakdown.	Ability to add or remove magnets to adjust headpiece strength.
Use of weaker magnet strength	Headpiece falls off patient's head frequently due to insufficient retention force.	Ability to add or remove magnets to adjust headpiece strength

- Residual risks:** All risk have been reduced as far as possible.
- Risk mitigation:** The risk controls are located in the table above. Additionally, the subjects will be instructed to discontinue use of the investigational headpiece immediately in the event that any discomfort is encountered. Subjects will always have access to their commercially approved hardware at all times during the study and will continue to use these commercially approved headpieces at the end of the visit.

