Primary Study Endpoint	Completion of all provided questionnaires that capture subjectively reported headpiece retention and comfort, as compared to baseline.
Primary Safety Endpoint	Cumulative frequency of adverse events and events per participant
Safety Parameters	Rate of adverse events
Control	Each participant will act as their own control
Research Hypothesis	The investigational headpiece and compatible magnets will provide participants with a retention option that is acceptable for daily use.
Study Schedule	Consent: Participants or will sign an informed consent form prior to the conduct of any study procedures. Baseline: Participants will complete a questionnaire regarding experience with their own headpiece at the time of consenting and enrollment. Follow up: Participants will evaluate the investigational headpiece during a chronic period of up to one-year or until the investigational headpiece receives FDA approval. They will complete questionnaires at two-month intervals. Off-Study: Participants will return their investigational headpieces to the Sponsor.
Experimental Hypothesis	A significant portion of study participants will report that the investigational headpiece is acceptable for wear during daily life.

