11.0 Appendix 2 Questionnaires

	Non-Significant Risk Study of a Cochlear Implant Headpiece Investigational Headpiece Baseline Questionnaire	[REDACTED] [REDACTED] [REDACTED] [REDACTED]
---	--	--

Subject ID: [REDACTED] - [REDACTED] Subject # - Subject initials (First, Middle, Last; if no middle initial, use a "-")	Visit Date: [REDACTED] Month [REDACTED] Day [REDACTED] Year
---	---

If you have any questions during the evaluation, please consult with the [REDACTED]
[REDACTED] [REDACTED]

Please indicate your rating:

1. Rate the retention of your personal headpiece				
Very Acceptable	Acceptable	No Opinion	Unacceptable	Very Unacceptable
				

2. Rate the comfort of your personal headpiece				
Very Acceptable	Acceptable	No Opinion	Unacceptable	Very Unacceptable
				

Thank you for your participation.

Non-Significant Risk Study of a Cochlear Implant Headpiece

Non-Significant Risk Study of a Cochlear Implant
Headpiece
Investigational Headpiece Fitting Form

Subject ID: -
Subject # - Subject initials
(First, Middle, Last; if no middle initial, use a "-")

Visit Date: -
 Month Day Year

To be completed by Study Staff:

Right Side	N/A 	Headpiece SN:
------------	---------------------------------	---------------

Left Side	N/A 	Headpiece SN:
-----------	---------------------------------	---------------

Study Staff (Print Name)	
Signature:	
Date:	

Non-Significant Risk Study of a Cochlear Implant Headpiece

	Non-Significant Risk Study of a Cochlear Implant Headpiece Investigational Headpiece Questionnaire	[REDACTED]
---	---	------------

Subject ID: [REDACTED] - [REDACTED] Subject # - Subject initials (First, Middle, Last; if no middle initial, use a "-")	Visit Date: [REDACTED] [REDACTED] - [REDACTED] [REDACTED] Month Day Year
---	---

Please refer to the following instructions during your time wearing the new headpiece.

1. Provide feedback on the headpiece and magnet configurations when requested.
2. If any headpiece discomfort arises during the study, please discontinue use of the investigational headpiece and resume use of your personal headpiece.
3. Return all investigational products to the Advanced Bionics Study Staff after the evaluation.

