If you have any questions, please consult with the [REDACTED]

Date questionnaire was completed: [REDACTED]

[REDACTED]-[REDACTED]-[REDACTED][REDACTED]

Month Day Year

Please rate:

1. Is retention of the investigational headpiece acceptable?

Very Acceptable	Acceptable	No Opinion	Unacceptable	Very Unacceptable
				

2. Is comfort of the investigational headpiece acceptable?

Very Acceptable	Acceptable	No Opinion	Unacceptable	Very Unacceptable
				

Thank you for your participation.

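### Participants told to stop wearing the headpiece at any discomfort may go on returning rating forms that show no wear item, so the forms cannot tell whether a rating reflects current wear

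*Protocol*

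**What the plan says.** **Stopping wear.** Protocol section 4.2 states that "the subjects will be instructed to discontinue use of the investigational headpiece immediately in the event that any discomfort is encountered". Instruction 2 on the Investigational Headpiece Questionnaire (Appendix 2) tells participants with discomfort to "please discontinue use of the investigational headpiece and resume use of your personal headpiece". Neither place asks them to report the stop.

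**Staying in the study.** Section 3.3 lists three reasons for discontinuation: withdrawn consent, a safety concern noted by a clinician, and inability to do what is needed to supply usable data. Stopping wear is not listed. Under section 3.4, participants receive enough forms at the outset to cover the study and post one back every two months. Section 3.6 pays for each form received and states no condition on wear.

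**What the form records.** The visible fields are "Date questionnaire was completed", a retention rating, and a comfort rating that asks "Is comfort of the investigational headpiece acceptable". Both ratings use a five-point scale whose middle choice is no opinion. No option for a headpiece that is not being worn is visible.

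**What the study wants to show.** The synopsis hypothesis is: "A significant portion of study participants will report that the investigational headpiece is acceptable for wear during daily life". The schedule says: "Participants will evaluate the investigational headpiece during a chronic period of up to one-year". The primary endpoint is "Completion of all provided questionnaires that capture subjectively reported headpiece retention and comfort, as compared to baseline".

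**The concern.** The study's claim is about daily wear over months. A rating given by someone wearing the headpiece is current evidence on that claim. A rating given from memory, by someone back on the commercial headpiece, is evidence of a different kind. If the form does not distinguish them, the report cannot say how many favourable ratings come from current wearers.

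Whether a stopper's rating misleads depends on the item. A person who stops for discomfort and rates comfort unacceptable has given a valid answer. The same person may also truthfully rate retention as very acceptable on every later form. The risk table in section 4.2 makes this plausible, because it links stronger magnets with skin irritation and pain. The two ratings are separate, and no visible item asks about acceptability for daily wear overall.

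A statistical analysis plan can choose the denominator and the handling of missing forms. It cannot recover wear status that was never collected. There is a secondary safety interest too: the primary safety endpoint counts adverse events, and a stop that nobody reports may be a discomfort event that is not counted.

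**Working it through.** **1. Can a stopper remain on the forms?** The form schedule runs for as long as participation lasts (section 3.4). Stopping wear does not by itself end participation (section 3.3), and payment follows the form (section 3.6). So a stopper may continue. This is inferred from the absence of an exit rule. The protocol does not say so outright.

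**2. Would the form show it?** The visible rating items are numbered 1 and 2 without a gap, and the visible redactions fall in the header, identifier, date and contact fields. On what can be read, there is no wear item. The date field dates the form, not the wear.

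**3. Would another record show it?**

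| Record | What it can show | Limit |
|---|---|---|
| Adverse event report (7.1) | Onset, action taken, outcome | Needs the discomfort to reach staff; scheduled follow-up is by post, extra meetings are on request, and non-serious events are looked at when monitoring takes place |
| Disposition log (3.3) | Completed, withdrew or discontinued | Study status, not wear status |
| Headpiece return (3.4) | Device is back | Due at the end of the study, so it need not date a stop |
| Final follow-up visit (mentioned in 7.1) | A chance to ask about wear | One late occasion; no wear question is specified |
| Primary endpoint (1.0) | Who returned every form | A former wearer who returns them all also meets it |

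Some stops will be captured. None of these records gives wear status at each rating.

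**4. Scale.** The protocol gives no expected stop rate, success threshold or sample-size calculation, so there is no planned figure to reproduce. On size it says: "A minimum of 20 participants will be enrolled in this present study, with a maximum of 200 participants". One participant therefore moves a share by 1/20 = 5 points or 1/200 = 0.5 points.

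**5. Illustration only; every count is assumed.** Take the retention item at one time point with n = 20: 14 acceptable, 2 not acceptable, 4 forms not returned. Let k be the number of the 14 who have permanently stopped for discomfort or poor retention.

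- Reported acceptable, missing counted as not acceptable: 14/20 = 70%, whatever k is.
- Sensitivity analysis counting those k as not acceptable: (14 − k)/20. For k = 0, 1, 2, 4 this is 70%, 65%, 60%, 50%.
- If k = 0 and all 4 non-returners are satisfied wearers: (14 + 4)/20 = 90%.

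Without a wear item, k is unknown. With it, k is known among returned forms. The 20 points between 70% and 90% come from unreturned forms (4/20), which the item alone does not resolve.

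**6. The pooled figure may lie on either side of the wearers' figure (also assumed counts).** With n = 200, 20 stopped, and 162 of 180 wearers rating acceptable, the wearers' share is 162/180 = 90.0%. The pooled share is 162/200 = 81.0% if all stoppers rate unacceptable and (162 + 20)/200 = 91.0% if all rate acceptable.

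**The case against.** The strongest reply is that the hypothesis concerns what participants report, not whether they are wearing the device. On that wording the 70% in the example stays at 70% for every k, and a composite of wearing the headpiece and finding it acceptable is an outcome that the protocol does not define. This stands. It is why the composite belongs in a sensitivity analysis and not in place of the planned result.

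Second, the path to a misleading comfort rating is narrow. The instruction is to stop for discomfort, and the form asks about comfort directly. Someone would have to stop, keep posting forms, rate comfort acceptable and never reach the staff. This stands for comfort. It does not hold for retention, which a person who stopped for discomfort can honestly rate well.

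Third, stopping may be temporary. Magnet changes and adjustments are available on request at any time (section 3.4), so a simple split into current and former wearers is too coarse. This stands, and the proposed item asks about it.

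Fourth, other contacts exist. Adverse events are monitored throughout (section 7.0), a final follow-up visit is mentioned (section 7.1), and a lasting non-wearer might be discontinued under the usable-data criterion. These reduce the gap. They do not give wear status form by form, and the protocol does not say that stopping wear meets that criterion.

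**Conclusion.** The point holds as a gap in data collection fixed by the protocol's own form: the visible form cannot show whether a rating reflects current wear, and the other records fill this only in part. The size is unknown. It is zero if nobody stops, or if every stopper rates both items unacceptable.

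The conclusion rests on two assumptions: that some stoppers go on returning forms, and that no redacted field asks about wear.

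A reader might infer three stronger things that the documents do not support:

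- That acceptability will be overstated. Neither the number of stoppers nor their ratings can be known from the plan, and the direction can go either way.
- That stoppers are required to keep returning forms. The protocol is silent on this.
- That a fixed number of forms is affected. Twelve months at two-month intervals gives 12/2 = 6 posted forms each, hence 6 × 20 = 120 to 6 × 200 = 1,200. But section 3.3 lets participation vary with enrolment date and FDA approval, so this total is not set by the protocol.

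This is an inexpensive improvement worth making before the data are collected, because missing wear status cannot be reliably recovered afterwards. It does not invalidate the study.

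**What to change.** 1. Add one item to each two-monthly form: *Are you currently wearing the investigational headpiece? If not, give the date stopped, the main reason, and whether the stop is temporary or permanent.*
2. Keep the stop instruction as it is, and add to form instruction 2: *tell the study staff and keep returning this form.* This also helps adverse event capture.
3. Report the retention and comfort ratings as planned among all fitted participants, and show them by wear status.
4. Add a sensitivity analysis that counts permanent stopping for discomfort or poor retention as not acceptable.

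The cost is one more item on an existing form, one more line of instruction, and a figure that may come out less favourable. The item gives no information on forms that are never returned. If that matters, a telephone call with the same question when a form is missing could use the contact details already taken at consent (section 3.4).
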